**LIST OF ABBREVIATIONS AND RELEVANT DEFINITIONS**

ABR	General Assessment and Registration form (ABR form), the application form that is required for submission to the accredited Ethics Committee; in Dutch: Algemeen Beoordelings- en Registratieformulier (ABR-formulier)
AE	Adverse Event
AR	Adverse Reaction
CA	Competent Authority
CCMO	Central Committee on Research Involving Human Subjects; in Dutch: Centrale Commissie Mensgebonden Onderzoek
CNS	central nervous system
CV	Curriculum Vitae
DSMB	Data Safety Monitoring Board
ERCP	Endoscopic Retrograde Cholangio-Pancreatography
EU	European Union
EudraCT	European drug regulatory affairs Clinical Trials
GCP	Good Clinical Practice
GDPR	General Data Protection Regulation; in Dutch: Algemene Verordening Gegevensbescherming (AVG)
IB	Investigator's Brochure
IC	Informed Consent
IMP	Investigational Medicinal Product
IMPD	Investigational Medicinal Product Dossier
METC	Medical research ethics committee (MREC); in Dutch: medisch-ethische toetsingscommissie (METC)
pCCA	Perihilar Cholangiocarcinoma
(S)AE	(Serious) Adverse Event
SEMS	Self-Expandable Metal Stent
SPC	Summary of Product Characteristics; in Dutch: officiële productinformatie IB1-tekst
Sponsor	The sponsor is the party that commissions the organisation or performance of the research, for example a pharmaceutical company, academic hospital, scientific organisation or investigator. A party that provides funding for a study but does not commission it is not regarded as the sponsor, but referred to as a subsidising party.
SUSAR	Suspected Unexpected Serious Adverse Reaction

---

UAVG	Dutch Act on Implementation of the General Data Protection Regulation; in Dutch: Uitvoeringswet Algemene verordening gegevensbescherming
WMO	Medical Research Involving Human Subjects Act; in Dutch: Wet Medisch-wetenschappelijk Onderzoek met Mensen

---

**SUMMARY**

**Rationale:** Most patients with perihilar cholangiocarcinoma (pCCA) are ineligible for curative-intent resection because of metastatic disease, locally advanced disease, or due to comorbidity. The key to successful palliative treatment is adequate biliary drainage to improve the patient's wellbeing and to allow for palliative systemic therapy. Endoscopic biliary drainage with plastic stents is the most common technique in the Netherlands. The main problem of this approach is that the stents cause bacterial colonization of the previously sterile intrahepatic bile ducts, because the stents cross the ampulla. Cholangitis often develops, especially if undrained segments become colonized. This is reflected by a 35% mortality within 3 months after diagnosis in patients who are ineligible for curative-intent resection. Most of these patients die from biliary obstruction and cholangitis without known metastatic disease. The only method to avoid colonization of the bile ducts is percutaneous placement of uncovered self-expandable metal stents (SEMS) that do not cross the ampulla.

**Objective:** To proof safety and effectiveness of direct percutaneous SEMS placement for palliative treatment of primary malignant perihilar stricture.

**Study design:** We aimed to perform a proof-of-concept pilot study at Erasmus MC , including 10 patients. The expected inclusion period was 1 year. Now all patients have been included in the pilot cohort and feasibility and safety has been determined, an expansion cohort will be added which includes UMC Utrecht, Amsterdam UMC and Oslo University Hospital (Norway), as participating centers in order to perform a multicenter phase-II trial. The aim is to assess the effectiveness and further assess safety of direct SEMS placement for palliative treatment of a primary malignant perihilar stricture. In total 67 patients will be included and analyzed in this study.

**Study population:** Patients with unresectable primary malignant perihilar obstruction on imaging with histopathological confirmation or high clinical suspicion (as determined by the multidisciplinary hepatobiliary team) who did not undergo previous endoscopic or percutaneous drainage procedures and who have no signs of cholangitis.

**Intervention:** Percutaneous transhepatic biliary drainage, by bridging significant ductal obstruction by self-expandable fenestrated metal stents without cannulation of the ampulla.

**Main study parameters/endpoints:** 6-month overall survival (OS), stent-related complications according to Clavien-Dindo grading system within 90 days (see Table 2.), absolute and relative

(%) bilirubin decrease after 14 days, the number of scheduled and unscheduled reinterventions within 90 days and quality of life.

**Nature and extent of the burden and risks associated with participation, benefit and**

**group relatedness:** The percutaneous intervention is an alternative approach to the standard of care, which is endoscopic biliary drainage. Complications due to the transhepatic biliary drainage, i.e. bleeding, infection and bile leakage are uncommon (<5%).

We hypothesize that direct SEMS placement in patients with unresectable primary malignant perihilar obstruction minimizes post-drainage cholangitis and mortality, requires fewer reinterventions, and increases the rate of patients receiving palliative chemotherapy.

In this study, patients will undergo an invasive procedure with hospital discharge after a few days. This corresponds to the standard of care. Follow-up appointments are planned 14 days (T1), one month (T2) and three months (T3) after stent placement. These visits will take 30 minutes. T2 and T3 are extra visits compared to standard of care.

## 1. INTRODUCTION AND RATIONALE

Perihilar cholangiocarcinoma (pCCA) is the most common malignancy of the bile ducts. Unfortunately, most patients are ineligible for curative-intent resection because of metastatic disease, locally advanced (i.e. unresectable) disease, or co-morbidity precluding a major liver resection. In the palliative setting, the median overall survival is only 6-10 months (1-3).

The key to successful palliative treatment is adequate biliary drainage to improve the patient's wellbeing and to allow for palliative systemic therapy. Discussion remains whether palliative biliary drainage is best achieved percutaneously or endoscopically (4-6). Regardless of a percutaneous or an endoscopic approach, biliary drainage for pCCA has a high risk of post-drainage cholangitis and most patients require multiple reinterventions to improve biliary drainage (1, 7). As a result of these complications, 90-day mortality was 35% after initial palliative drainage in 186 patients with (suspected) unresectable pCCA in the Netherlands (1). Notably, the majority of patients with 90-day mortality have no metastatic disease, suggesting that mortality is mainly caused by insufficient biliary drainage and/or drainage-related complications (1). Failure of current management of biliary obstruction in unresectable pCCA is also reflected by the very low percentage (<10%) of patients who receive palliative systemic chemotherapy.

Endoscopic biliary drainage with plastic stents in one or more segments of the liver is the most common technique in the Netherlands (1). The main problem of this approach is that the stents cause bacterial colonization of the previously sterile intrahepatic bile ducts, because the stents cross the ampulla. Cholangitis often develops, especially if undrained segments become colonized. Percutaneous transhepatic biliary drainage is the alternative approach. External biliary drainage can be accomplished without passing the tumor and the ampulla. The drawback of external-only drainage is that patients typically dehydrate and develop metabolic disturbance. The bile fluids can be readministered with a nasoduodenal feeding tube. However, such a tube impacts the quality of life. Moreover, cholangitis can still develop from skin bacteria gaining access to the biliary tree with external biliary drainage. Also, external drainage suffers from a high risk of catheter dislodgement. Therefore, percutaneous biliary catheters are typically internalized: that is, side holes in the intrahepatic part of the catheter collect the bile and deliver the bile via the tip of the catheter which is positioned beyond the ampulla in the duodenum. The downside of an internalized percutaneous biliary catheter is the same as an endoscopic plastic stent: the ampulla is crossed and biliary bacterial colonization occurs. Percutaneously placed catheters are typically flushed with normal saline to avoid clogging of the side holes. However, flushing has the theoretical downside of causing colonized bile to end up in undrained segments and cause cholangitis.

The only method to avoid colonization of the bile ducts is percutaneous placement of uncovered self-expandable metal stents (SEMS) that do not cross the ampulla. After stent placement, the tract is sealed (e.g., with glue) without leaving a catheter.

Only patients with resectable or unresectable perihilar malignancy are eligible for SEMS placement, since it is not possible to endoscopically remove a SEMS and long-term effects of a SEMS for benign disease are unknown. However, a frequent diagnostic challenge is the distinction of benign and malignant biliary duct strictures. Benign diseases, such as Mirizzi Syndrome and IgG4-related sclerosing cholangitis, can mimic perihilar malignancy as well.(11, 12) In many patients with suspected pCCA, histological confirmation of malignant disease is lacking at the time of the first drainage procedure. In these patients, the probability of the stricture being malignant is then estimated based on clinical symptoms by the multidisciplinary hepatobiliary team.

Painless jaundice is the presenting symptom in 90% of pCCA patients. Fifty-six percent of pCCA patients have systemic signs of malignancy (i.e., anorexia, weight loss, and fatigue) at their initial presentation.(8) Jaundice can also be present in advanced gallbladder cancer or intrahepatic cholangiocarcinoma, 30% and 20% at presentation, respectively.(9, 10) When a suspicion of a primary malignant perihilar stricture is seen on imaging, it can be difficult to distinguish these different entities.

Absence of systemic signs of malignancy and fluctuation or spontaneous decrease of a total bilirubin level before start of any treatment can suggest potential benign origin. If a combination of high suspicion of primary malignant perihilar obstruction on imaging and an increasing total bilirubin level is present, according to unpublished data from our own center only a very small number of cases (less than 5%) will eventually turn out to be benign disease. Histological confirmation can be obtained through frozen section procedure before the SEMS is placed, when there is any doubt of malignant disease. During the procedure biopsies and brushes can be performed on default to obtain tissue diagnosis.

We hypothesize that direct SEMS placement in patients with unresectable primary malignant perihilar obstruction minimizes post-drainage cholangitis and mortality, requires fewer reinterventions, and increases the rate of patients receiving palliative chemotherapy.

## 2. OBJECTIVES

Primary Objectives:

- 6-month overall survival (OS).

Secondary Objective(s):

Pilot Cohort and overall analysis

- Stent-related complications according to Clavien-Dindo grading system within 90 days (see Table 2.);
- Absolute and relative (%) bilirubin decrease after 14 days;
- Number of scheduled and unscheduled reinterventions within 90 days.
- Infectious biliary complications (i.e. cholangitis and cholecystitis);
- Technical success of stent placement at initial drainage procedure;
- Bile culture results;
- Proportion of patients that started with palliative chemotherapy;
- Cost-effectiveness.

Expansion cohort

- Quality of Life (QoL).

### 3. STUDY DESIGN

#### Pilot cohort (10 patients)

In preparation of the design of a phase-II study, we aim to perform a proof-of-concept pilot study at Erasmus Medical Center, Rotterdam, The Netherlands, including 10 patients in order to proof safety and feasibility of direct SEMS placement for palliative treatment of a primary malignant perihilar stricture. The expected inclusion period is one year. After the pilot we will evaluate the safety and feasibility of the method as well as complication rates. Based on our findings we will amend the protocol before continuing with the formal phase-II trial.

#### Expansion cohort (27 patients)

After the inclusion of the first 10 patients has been completed, an expansion cohort will be added in which UMC Utrecht, Amsterdam UMC and Oslo University Hospital as participating centers will be added, in order to perform a multicenter phase-II trial. Following the analyses of the first 10 patients, another 27 patients will be included to assess the effectiveness and safety of direct SEMS placement for palliative treatment of a primary malignant perihilar stricture. In total 37 patients will be included and analyzed for the study endpoints. The expected inclusion period of the additional 27 patients is two years.

#### Second expansion cohort (30 patients)

Nine months (July 1st, 2022) after approval for the first expansion cohort of 27 patients, we have included 20 additional patients in Erasmus MC. For the first 30 patients (10+20), the outcomes are compared with our historical cohort for endoscopic biliary drainage in Table 1.

Table 1

	Number of patients	Reintervention within 90 days	Mortality within 90 days	Administration of systemic chemotherapy
Endoscopic drainage – retrospective cohort	90	75%	35%	20%
Primary percutaneous stenting - TESLA trial	30	6%	3%	75%

Because of these favorable results, we are currently designing a multicenter randomized controlled trial (RCT) to compare this intervention with the standard of care (i.e. endoscopic biliary drainage). Six additional centers will participate in this trial. To avoid any aspect of

---

learning curve regarding the intervention within the RCT, each participating center is required to perform the study intervention in 5 patients in this phase II study, before accruing patients in the RCT. Therefore, a second expansion cohort of 30 patients (i.e. 5 patients per center for 6 centers) is required.

A total of 67 patients (10+27+30) will be included and analyzed for the study endpoints. The expected inclusion period of the additional 30 patients, in six participating centers, is one year.

## 4. STUDY POPULATION

### 4.1 Population (base)

Patients with high suspicion of a primary malignant perihilar stricture who cannot undergo a curative-intent resection are eligible for inclusion. Eligibility is established during the multidisciplinary meeting. The definitive diagnosis of pCCA is established based on histopathology from endoscopic or percutaneous ultrasound-guided biopsy or on cytology obtained using endoscopic brush or fine-needle aspiration from the primary tumor or from a metastasis. In absence of histopathological confirmation, the multidisciplinary hepatopancreaticobiliary team form an opinion on the probable diagnosis of pCCA based on clinical symptoms, radiological and endoscopic imaging and laboratory tests(13). Informed consent is obtained at the outpatient clinic.

### 4.2 Inclusion criteria

In order to be eligible to participate in this study, a subject must meet the following criteria:

- Written informed consent must be given according to ICH/GCP, and national/local regulations.
- Unresectable primary malignant perihilar obstruction on imaging with histopathological confirmation or high clinical suspicion (as determined by the multidisciplinary hepatobiliary team)

And

- Symptomatic hyperbilirubinemia (a combination of a total bilirubin level >20 mmol/l, and/or jaundice and/or loss of appetite and/or dark urine and/or steatorrhea)

### 4.3 Exclusion criteria

A potential subject who meets any of the following criteria will be excluded from participation in this study:

- Fluctuation or spontaneous decrease of a total bilirubin level before start of any treatment suggesting potential benign origin.
- Patients who underwent previous drainage procedures endoscopically or percutaneously with an internalized biliary catheter.
- Clinical signs of cholangitis. Cholangitis was defined as both fever (i.e. body temperature >38.5°C) and leucocytosis (i.e.  $\geq 10 \times 10^9/L$ ) without clinical or radiological evidence of acute cholecystitis (14). Patients who underwent ERCP are eligible, providing no papillotomy was performed or stent was placed and there are no signs of cholangitis.

#### 4.4 Sample size calculation

##### Pilot cohort (10 patients)

A total of 10 patients will be included in this pilot study. This number will be sufficient to investigate treatment feasibility and to identify any bottlenecks in the protocol that should be adjusted for the definitive trial protocol. Taking into account that pCCA is a rare disease, the number of 10 patients will ensure a feasible time frame.

##### Expansion cohort (27 patients)

To detect a 20% mortality decrease compared with our historical cohort (45% mortality within 6 months) we need to include 37 patients using an alpha of 0.05 and power of 80%. We expect to finish patient accrual within two years.

Following the very promising results in the first 10 patients, another 27 patients will be included to assess the effectiveness and safety of direct SEMS placement for palliative treatment of a primary malignant perihilar stricture.

Taking into account that pCCA is a rare disease, another 27 patients will ensure a feasible time frame for study completion.

##### Extra expansion cohort (30 patients)

We want all current and future participating centers to perform the intervention in 5 patients in this study before entering the upcoming RCT. For this reason, another 30 patients will be included to assess the effectiveness and safety of direct SEMS placement for palliative treatment of a primary malignant perihilar stricture. The expected inclusion period of the additional 30 patients, in at least four participating centers, is one year.

Total cohort:  $10 + 27 + 30 = 67$  patients.

## 5. TREATMENT OF SUBJECTS

### 5.1 Investigational product/treatment

Preprocedural intravenous antibiotic prophylaxis is administered (cefuroxime 1500 mg/metronidazole 500 mg; conform institutional ERCP protocol). Procedural sedation and analgesia is performed. An interventional radiologist performs the procedure: (1) ultrasound- and fluoroscopy guided percutaneous transhepatic biliary drainage, (2) bridging significant ductal strictures with a wire and catheter and (3) placement of an uncovered SEMS, (4) without cannulation of the ampulla. Bile cultures are routinely taken. Depending on the tumor size and its localization, right intercostal and/or left epigastric access is chosen. The initial percutaneous transhepatic bile duct puncture is performed with a 21G Chiba needle. Then, a Neffset sheath is placed (Cook Medical) and using a 0.032-0.038 inch glideguidewire with 4 Fr catheter is advanced through the bile duct stricture without passing the ampulla. After crossing the stricture, the guidewire is preferably replaced by a stiff Amplatz guidewire. The Neffset sheath is replaced by a vascular sheath that accommodates the biliary stent (7 or 8Fr). Before stent insertion, the stricture (occlusion) is dilated with a balloon catheter that is pulled over the guidewire (diameter 6 to 8 mm). Then, a biliary stent (HILZO Biliary stent, uncovered straight type, 10mm diameter and 6 or 8cm length) is inserted, still with the wire not passing the ampulla. Bilateral stents are placed when suboptimal drainage of contralateral bile ducts is seen after placement of a single uncovered SEMS. The tract is sealed with Avitene (BD, NJ, USA) mixed with 8 ml of iodine contrast agent without leaving an external drain, unless the SEMS is not sufficiently expanded. When histological confirmation is lacking, during the same procedure percutaneous (forceps) biopsies and brush cytology are taken to confirm the presence of pCCA by frozen section before SEMS-placement, in order to prevent placement of (non-removable) SEMS in patients who have potentially non-malignant disease. Whenever the stricture cannot be passed with a wire, and stent placement is not feasible, an external biliary drain is placed. Crossing of the ampulla is still not performed (no internal-external drainage). A second attempt of recanalization and stenting is performed after 3 or more days.

Intravenous antibiotics (cefuroxime 1500 mg/metronidazole 500 mg) are routinely administered during hospitalization. After discharge oral antibiotics (Amoxicillin/clavulanate 500/125 mg) are administered during five days.

The radiologist reports whether stent placement was technically successful, and whether a second drainage procedure is indicated (e.g., in case the stricture cannot be passed in the first attempt). Primary technical success is defined as successful passage of the stricture and stent placement. Successful drainage is defined as a bilirubin below 50 mmol/l or a

---

reduction in bilirubin level of at least 50% within 14 days after drainage. Secondary technical success is defined as successful passage of the stricture and stent placement 3 days or more after the initial procedure.

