#### 8.1.2 Secondary study parameters/endpoints

- Stent-related complications according to Clavien-Dindo grading system within 90 days (see Table 2.).
- Absolute and relative (%) bilirubin decrease after 14 days.
- Number of scheduled and unscheduled reinterventions within 90 days.
- Infectious biliary complications (i.e. cholangitis and cholecystitis);
- Technical success of stent placement at initial drainage procedure;
- Bile culture results;
- QoL, measured with the EORTC Quality of Life Questionnaire C-30 (QLQ-C30) and its biliary cancer module (QLQ-BIL21) (see Appendix C and D);
- Proportion of patients that became eligible for palliative chemotherapy, based on bilirubin level below 20 mmol/l and good performance status (ECOG < 2);
- Cost-effectiveness.

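### The three absolute bilirubin thresholds are printed in mmol/l, where micromol/l is almost certainly meant; as written they separate no patients, and the drainage-success limit also overlaps the entry range

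*Protocol*

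**What the plan says.** The protocol sets an absolute bilirubin threshold in three places, each time in mmol/l, and gives bilirubin in no other unit.

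- **Entry (4.2).** Symptomatic hyperbilirubinemia is "a combination of a total bilirubin level >20 mmol/l, and/or jaundice and/or loss of appetite and/or dark urine and/or steatorrhea".
- **Drainage success (5.1).** "Successful drainage is defined as a bilirubin below 50 mmol/l" or, as the alternative, a "reduction in bilirubin level of at least 50% within 14 days after drainage". Meeting either limb is enough.
- **Chemotherapy eligibility (8.1.2).** The proportion who became eligible is judged "based on bilirubin level below 20 mmol/l and good performance status (ECOG < 2". Both conditions must hold.

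One listed bilirubin endpoint uses no threshold: "Absolute and relative (%) bilirubin decrease after 14 days" (8.1.2, also in section 2).

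**The concern.** Serum bilirubin is a matter of micromoles per litre. A limit of 20 or 50 mmol/l lies beyond any level a patient can have, so a rule built on it gives the same answer for everyone. That touches an eligibility limb, a success definition and a listed secondary endpoint. Because the unit is the same in all three places, no section of the protocol corrects another. The paragraph on case report forms in 12.1 says that the data collected are derived from the protocol, so the unit could pass into field labels or range checks.

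A second question remains once the unit is right. The entry limit (20) lies below the success limit (50), and the two success limbs are joined by an or. Some patients could then satisfy the success level before anything has been done to them.

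**Working it through.** There is no calculated figure in the protocol to reproduce. The check is a unit conversion, followed by applying each rule to a range of levels.

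**Inputs.** The thresholds 20, 50 and 20 come from sections 4.2, 5.1 and 8.1.2. The molar mass follows from the formula C33H36N4O6: 33 × 12.011 + 36 × 1.008 + 4 × 14.007 + 6 × 15.999 = 584.7 g/mol. The protocol gives no patient bilirubin values, so levels from 5 to 1000 micromol/l are assumed.

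**Step 1: what the printed limits mean.** Concentration in g/l = mol/l × 584.7.

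- 20 mmol/l: 0.020 × 584.7 = 11.7 g/l, or 1169 mg/dl.
- 50 mmol/l: 0.050 × 584.7 = 29.2 g/l, or 2923 mg/dl.
- In micromol/l the same numbers are 1.17 and 2.92 mg/dl, smaller by a factor of 1000.

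The highest assumed level, 1000 micromol/l = 1 mmol/l, is still 20 times below the lower printed limit and 50 times below the upper one.

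**Step 2: apply each rule.**

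| Assumed level (micromol/l) | Entry >20, mmol/l | Success <50, mmol/l | Chemotherapy <20, mmol/l | Entry >20, micromol/l | Success <50, micromol/l | Chemotherapy <20, micromol/l |
|---|---|---|---|---|---|---|
| 5 | no | yes | yes | no | yes | yes |
| 20 | no | yes | yes | no | yes | no |
| 50 | no | yes | yes | yes | no | no |
| 100, 300, 500, 1000 | no | yes | yes | yes | no | no |

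The success and chemotherapy columns show the absolute bilirubin condition only. As printed, every column is constant. In micromol/l, each rule separates patients.

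**Step 3: entry against success.** This holds in any unit shared by the two limits. A baseline value b with 20 < b < 50 meets the bilirubin limb of entry and is already below 50. For example, a patient who enters at 30 and rises to 45 has a relative change of (45 − 30)/30 = +50%, yet counts as a success because 45 < 50. Patients admitted on a symptom alone may start at 20 or lower, and they too are already below 50.

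If k of n measured patients start below 50, up to k/n of the success rate can arise without any fall. With all 67 planned patients measured, each such patient is worth up to 1/67 = 1.5 percentage points. The protocol does not give k.

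**The case against.** The case for treating this as small is strong, and most of it stands.

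- **Entry.** A reader might infer that nobody qualifies. The documents do not support that. The items in 4.2 are joined by and/or, so jaundice or another symptom admits a patient, and section 3 reports 30 patients already included.
- **Drainage success.** A reader might expect a reported success rate of 100%. Successful drainage is defined in 5.1 but is not listed as an endpoint in sections 2, 8.1 or 10.2, and nothing shows that a site has applied the unit literally. Laboratory results would probably be read in micromol/l.
- **Chemotherapy.** Only 8.1.2 uses the bilirubin cut-off. Sections 2 and 10.2 name the proportion who started chemotherapy, which needs no threshold. One version of one secondary endpoint is affected.
- **Main results.** Overall survival, the sample size in 4.4 (based on 6-month mortality) and the 14-day bilirubin decrease do not depend on these limits.
- **Source of the error.** A micro sign misread as m when text is taken from the PDF cannot be fully excluded. Other special characters survive in section 4.3 (degree sign, ≥, ×), but no micro sign appears elsewhere to settle the matter.
- **Overlap of 20 and 50.** Combining a target level with a relative fall is a legitimate design choice, and very few patients may start below 50.

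These points limit the consequences. They do not make the printed thresholds usable, and they do not remove the overlap.

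**Conclusion.** The point holds in a limited form. All three absolute bilirubin thresholds are printed in a unit that makes them a thousand times the same number in micromol/l and puts them beyond any possible serum level. Read literally, the bilirubin limb of entry is met by nobody, the absolute limb of drainage success by every measured patient, and the eligibility endpoint in 8.1.2 measures ECOG < 2 alone.

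The practical effect is probably small, because sites are likely to read micromol/l and the main results use no threshold. This conclusion assumes that levels do not exceed about 1000 micromol/l, a limit that could be 20 times higher without changing any result, and that the PDF shows the same unit as the text.

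The overlap between entry and success is real as logic, but its size is unknown. It would be tempting to put a percentage on the automatic successes; the documents give no baseline distribution, so none is offered. Severity: minor to moderate.

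**What to change.** 1. Check sections 4.2, 5.1 and 8.1.2 against the PDF and, if mmol/l stands there, correct the unit to micromol/l in all three. The values 20 and 50 stay with the clinical team.
2. Check the bilirubin unit and range limits in the eCRF. The absolute 14-day decrease takes its unit from the same field.
3. Have the clinical team reconcile 4.2 with 5.1, so that it is clear whether a patient already below 50 before the procedure can count as a drainage success. No replacement rule is proposed here; for instance, applying different limbs above and below 50 at baseline would create a jump at 50 and set a new clinical definition.
4. Report any drainage-success rate together with the number of patients already below 50 at baseline.

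The cost is a text amendment, an eCRF check and one extra count in the report. Sample size, visits and primary analysis do not change.
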